1. STUDY OBJECTIVES

1.1 Primary Objective

The **primary objective** will be to study changes in putamen structural connectivity in healthy teens with meditation training. **Hypothesis**: Putamen structural node strength will increase in the training group compared to controls.

R61 Go/No-Go Criteria. Detect an effect size (a threshold of Cohen's d > 0.20) in changes of the primary mechanistic outcome (**Putamen structural node strength**) by the described meditation training in 100 healthy adolescents that are 14-18 years old and retain at least 80% of randomized participants for primary outcome measurement at the end of the study regardless of adherence to the intervention.

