- The study's pregnancy-related policy and procedure are as follows. First, all female participants will be asked to fill out a pregnancy screening questionnaire and then take a urine pregnancy test immediately prior to entering the MRI scanner room. Any subject that is either pregnant or might possibly be pregnant are not allowed to enter the MRI scanner room. Results of the urine pregnancy screening test will be shared with the adolescent subject only and not with the adolescent's parents or legal guardians. As per California state confidentiality laws, the results of pregnancy tests in minors cannot be shared with the minor's parent or legal guardian without the written permission of the minor. If the pregnancy test is positive, we will counsel the teen and give her referrals to teen pregnancy resources such as Planned Parenthood. If the participant is pregnant, the participant is not allowed to enter the study until the pregnancy is over. Second, if the participant who is in the intervention group becomes pregnant during the course of the study after the first MRI scan, she will be allowed to finish participating in the group intervention since there are no known potential adverse effects on the fetus due to meditation. However, although there are no known adverse negative effects of MRI scans on the fetus, we have decided to be conservative in our study and not allow participants who become pregnant during the study after the first MRI scan to have the second MRI scan in order to minimize any potential risk to the unborn fetus.
- Not allowable: Current mindfulness training (e.g. MBSR, MBCT, DBT) and/or practice with a typically sitting meditation or yoga of 20 or more minutes two or more times per week within 60 days prior to study entry.
- Potential adolescent subjects with current drug or alcohol use or dependence that, in the opinion of the site investigator, would interfere with adherence to the study requirements will be excluded and not allowed to enter the study. We will use the Brief Screener for Tobacco, Alcohol, and other Drugs (BSTAD) developed by National Institute on Drug Abuse

- (NIDA) to determine higher risk subjects who will be excluded: https://www.drugabuse.gov/adolescent-substance-use-screening-tools.

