9.2. Sample Size and Randomization

The study is powered for medium-large effect size of the meditation training on the putamen node strength. With type I error of 0.05, type II error of 0.2 (power of 80%), two-sided effect size of a Cohen's D of 0.6, the required sample size is N=45 subjects who will be studied before and after the TARA training. Given the length of the study (three months), the required commitment to participation in the training, and based on our experience, we assume an attrition rate of 10%; therefore, the target sample size is 50 subjects per group. Our primary analysis will be a general linear model of putamen node strength at week 12 with terms for baseline node strength, treatment assignment and participant sex. The primary analysis will be intent to treat and will include all randomized participants regardless of treatment receipt or protocol violations.

The only clustering in the trial will be the group delivery of the TARA intervention. We anticipate 4 TARA classes of 10-15 participants. We expect the intraclass correlation to be negligible for the following reasons: a) the TARA instructors are trained in standard procedures, b) we expect formidable individual level variation. We therefore did not include cluster assignment in the sample size calculation. We are going to test this assumption in a sensitivity analysis which extended the primary analysis by inclusion of treatment by TARA class interaction.

To standardize TARA delivery, we have included facilitator training and created a very detailed TARA manual (please see Appendix).

Treatment Assignment Procedures

We will use computer-generated randomization with variable blocks sizes of 4, 6 and 8. Individuals will be randomized with no stratification or restricted except the permuted blocks. We will permute 8 blocks of size 8, 2 blocks of size 6, and 4 blocks of size 4. The treatment assignments will be 1:1 within each block and assignments within a block will be permuted. The only masking will be in the administration of questionnaires and in the interpretation of putamen node strength.

The rationale for the use of randomization is to minimize potential biases.

The study is open label to participants, and thus there is no need for unblinding or unblinding procedures.

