9.6 Data Analyses

Primary Outcome. To attain the primary objective, we will test the hypothesis that an increase in the node strength of the putamen (dependent variable) will be observed in the training group compared to the controls. This hypothesis will be tested using an analysis of covariance (ANCOVA) accounting for sex and fit by maximum likelihood. Stata (College Station, TX) will be used to perform data analyses. The use of maximum likelihood mitigates susceptibility to missing data. Examination of variable distribution and outlier identification will be performed. We will additionally explore age, pubertal status (as determined by the Tanner stage self-report form (Tanner et al., 1962)), and pre-training associations with the changes through an examination of interaction. Potential pre-/post-training differences in movement during MRI will be accounted for by assessing the number of rejected diffusion directions. Sex as a biological variable: In all analyses described, sex will be included as a factor, we will also test for a randomized arm by sex interaction.

The only clustering in the trial will be the group delivery of the TARA intervention. We anticipate 4 intervention arm clusters of 10-15 participants. We expect the intraclass correlation to be negligible for the following reasons: a) the TARA instructors are trained in standard procedures, b) we expect formidable individual level variation. We are going to test this assumption in a sensitivity analysis which extended the primary analysis by inclusion of treatment by TARA class interaction. We are going to test this assumption in a sensitivity analysis which extended the

primary analysis by inclusion of treatment by TARA class interaction.

To standardize TARA delivery, we have included facilitator training and created a very detailed TARA manual (please see Appendix).

In addition, we will examine relationship between changes in node strength of the putamen and adherence to sessions, proportion of sessions attended, by performing a Spearman rank correlation of TARA adherence (by percentage of sessions attended) and change in node strength. We will use ANCOVA analysis with a treatment by attendance interaction to estimate the putamen node strength which would be achieved with full attendance in all training session.

Secondary Outcome.

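### Maximum likelihood does not cover a missing second scan: the primary ANCOVA is a completers' estimate, although the plan says it includes all randomized participants

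*Combined protocol and SAP*

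**What the plan says.** Section 9.2 makes the primary model a general linear model for week-12 putamen node strength, with baseline node strength, arm and sex as terms. On the analysis set it says: "The primary analysis will be intent to treat and will include all randomized participants regardless of treatment receipt or protocol violations". Section 9.3 defines the intent-to-treat population in the same way.

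Section 9.6 calls the model an ANCOVA fitted by maximum likelihood and adds: "The use of maximum likelihood mitigates susceptibility to missing data". The plan gives no imputation rule, no missing-at-random statement and no missing-data sensitivity analysis. The one sensitivity analysis it names concerns TARA class. Retention is tabulated and compared between arms by Fisher's exact test, but nothing follows from the result.

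The schedule in Section 6.1 has MRI at Visit 1 and Visit 14 only.

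On expected loss, Section 9.2 says "we assume an attrition rate of 10%; therefore, the target sample size is 50 subjects per group". The Go/No-Go criteria in Section 1.1 require the trial to "retain at least 80% of randomized participants for primary outcome measurement" and to show a Cohen's d above 0.20. Section 4.2 decides to "not allow participants who become pregnant during the study after the first MRI scan to have the second MRI scan". Against that, Sections 6.2.1, 6.2.5 and 8 ask for the final-visit assessments, MRI included, from those who leave or stop the intervention early.

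**The concern.** Likelihood methods help with missing outcomes when the participant has other outcome data to borrow from, such as earlier post-baseline visits. This trial has a single post-baseline scan. The promise to include everyone and the model chosen to do so therefore do not fit together, and the sentence offered as the safeguard describes a property the model lacks.

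The Go decision for the next phase rests on whether d exceeds 0.20, so a modest shift in the estimate can change it. The plan also gives a reason to doubt that the missing resemble the rest. Section 9.6 examines node-strength change against attendance, and Section 2.2 reports a preliminary correlation with the amount of practice. The trial is open label with a waitlist. If TARA participants who attend little are also less likely to return for the scan, the loss is specific to one arm and related to gain. Attendance is recorded but is not in the primary model.

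**Working it through.** **1. The plan's own sample size.** Inputs (Section 9.2): "With type I error of 0.05, type II error of 0.2 (power of 80%), two-sided effect size of a Cohen's D of 0.6".
- Normal approximation: n per arm = 2 × (1.96 + 0.84)² / 0.6² = 43.6, so 44. The two-sample t calculation gives 44.6, so 45.
- Attrition: 45 / 0.90 = 50 per arm.
- Both figures reproduce. The inflation already treats the lost 10% as giving no information.
- Power at d = 0.6 by two-sample t: 84.4% with 50 per arm, 80.4% with 45, 75.5% with 40 (20% loss).

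**2. What the likelihood does with a missing second scan.** Write b for baseline and y for week 12. A participant's contribution is f(b | sex, arm) × f(y | b, arm, sex). If y is missing, the second factor integrates to 1. The first does not involve the arm effect on y given b. That effect is therefore estimated by least squares on participants with y observed.

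Numerical checks, simulated with 50 per arm and about 20% of outcomes missing:
- Full likelihood keeping all baselines gave 0.62439; least squares on completers gave 0.62439.
- In three further datasets the ANCOVA effects were 0.46392, 0.49493 and 0.67030. None changed when the baselines of participants without y were shifted by 3 SD.
- In the same datasets a joint baseline and week-12 likelihood model, with baseline means free or constrained equal, gave the same values to five decimals. Recasting the model as a two-time-point mixed model does not help.

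**3. When the completers' estimate is sound.** With loss completely at random and true d = 0.6 (3,000 simulations per setting; assumed baseline–follow-up correlation 0.5, 0.7 or 0.9), the mean estimate was 0.597 to 0.601. Its SD was about 5–6% larger than with full data at 10% loss and 10–13% larger at 20%. The cost there is precision, not bias.

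**4. Limiting case.** Assume a proportion m of the TARA arm is missing and had no gain, and that missing waitlist participants resemble those observed. Then d(all randomized) = (1 − m) × d(completers).

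| m | d over all if completers' d = 0.60 | completers' d at which d over all = 0.20 |
|---|---|---|
| 10% | 0.9 × 0.60 = 0.54 | 0.20 / 0.9 = 0.22 |
| 20% | 0.8 × 0.60 = 0.48 | 0.20 / 0.8 = 0.25 |

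Simulation gave the same bias at true d = 0.6: about +0.06 and +0.12.

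**5. A milder case (all inputs assumed).** Of the TARA arm, 80% attend 90% of sessions and 20% attend 25%. Gain is proportional to attendance. High attenders miss the scan 5% of the time, low attenders 50% or 80%.
- TARA loss: 0.8 × 0.05 + 0.2 × 0.5 = 14%, or 0.8 × 0.05 + 0.2 × 0.8 = 20%.
- Mean attendance, whole arm: 0.8 × 0.90 + 0.2 × 0.25 = 0.77.
- Mean attendance among those scanned: (0.76 × 0.90 + 0.10 × 0.25) / 0.86 = 0.824, or (0.76 × 0.90 + 0.04 × 0.25) / 0.80 = 0.868.
- Inflation: 0.824 / 0.77 = 1.07, or 0.868 / 0.77 = 1.13.

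Simulation with baseline correlation 0.7 and 10% waitlist loss agreed: a true d of 0.46 was estimated as 0.49 to 0.52. With true d about 0.20, the chance of observing d above 0.20 rose from 51% to 57% in the worse case.

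**The case against.** The strongest reply is that the plan protects itself by design. Those who leave or stop early are still to have the Visit 14 scan, and retention is judged regardless of adherence. Participants who stop attending but return for the scan are the very people these rules target. The all-randomized wording is also usual intent-to-treat language against excluding non-compliers, and the sample size already discounts 10%. All of this stands as a reason why loss may be small. It does not make the maximum-likelihood sentence true, and the plan still budgets for loss.

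Three stronger readings are tempting, and the documents do not support them:

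- *Every listed reason for early termination means no scan.* Section 6.2.5 gives moving away, accident and illness as reasons for leaving, directly after asking for final assessments from early leavers. Only pregnancy, in Section 4.2, expressly rules the second scan out.
- *Maximum likelihood does nothing at all.* A joint fit could keep a participant whose baseline is missing. That is conceivable here: randomization falls on the day of the baseline assessment (Section 6.2.2), and Section 9.6 anticipates rejected diffusion directions. The failure concerns missing week-12 outcomes.
- *Imputation from sessions attended should become the primary estimate.* In the milder case above, it removed most of the bias but had slightly larger root mean squared error (0.159–0.180 against 0.156–0.170 for completers). In the worse setting about 12–13% of simulated trials had no scanned low attender to impute from. Its good performance also depends on gain having been simulated as proportional to attendance.

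**Conclusion.** The concern holds. For missing week-12 scans, the maximum-likelihood statement is wrong for this model, and the primary result will be a completers' ANCOVA under an all-randomized label. That conclusion follows from the model and the two-scan schedule and needs no assumption about why scans are missing.

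The size of any bias is conditional. There is none if missingness depends only on arm, baseline and sex and the model is correct. Under the assumed attendance mechanism, d is 7–13% too high. In the no-gain limiting case, completers' values of d up to 0.22 (10% loss) or 0.25 (20% loss) would pass the Go threshold wrongly.

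A reader might infer that the primary effect will be inflated, or that 10–20% of participants will be lost. Neither is established. The 10% is a planning assumption, the 20% is the most the retention criterion allows, and the direction of bias depends on who misses the scan. The defect is that the plan neither states the assumption it relies on nor tests it near the decision threshold.

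**What to change.** 1. In Section 9.6, replace the maximum-likelihood sentence with a statement that the ANCOVA uses participants with a Visit 14 value and is valid if missingness depends only on arm, baseline and sex. Align the analysis-set sentence in Section 9.2 with it.
2. Prespecify one sensitivity analysis over all randomized participants. Multiply impute missing Visit 14 node strength in the TARA arm from the waitlist distribution given baseline and sex (no gain), and in the waitlist arm from its own distribution. Fit the same ANCOVA to each imputed set, combine the results, and report d beside the 0.20 Go threshold.
3. Do the same for the SDQ, which uses the same ANCOVA, where it is missing. The loss may be smaller there: the questionnaire is electronic and the pregnancy rule bars only the MRI.
4. Imputation using sessions attended (available in the TARA arm only) may be a further sensitivity analysis, not a replacement for the primary estimate.

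The cost is SAP wording and a few lines of Stata, with no new data collection. The downside is a little more analysis work and a possibly less favourable d to report.

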6.2.2 Enrollment, Baseline, and/or Randomization

Enrollment

The current study will utilize a single informed signed consent form that describes both screening and study procedures. Thus, in the current study, the enrollment date is defined as the date all of the screening criteria are met and the individual agrees to participate which is also the same date as the randomization date (i.e., Visit 1 [Day 0]). Please see above, Section 6.1, Schedule of Evaluations Table. The enrollment date will be recorded on a case report form (please see included Randomization and Enrollment form) along with the allowable window between screening and randomization (please see above section, "Screening", for the precise allowable time window between screening and randomization).

Baseline Assessments

The following baseline evaluations will occur on Visit 1 (Day 0) of the study:

MRI brain scan. An MRI brain scan will be acquired at baseline to compare

- against the final MRI brain scan that will be obtained at the final visit (Visit 14).
- Strengths and Difficulties Questionnaire (SDQ). Emotional problems will be assessed in all participants at baseline using the SDQ in order to compare with the SDQ that will be collected at the final visit (Visit 14).

Randomization

Computer-generated randomization will precede intervention administration in the current randomization study. The time window for randomization relative to completion of screening and baseline will be 24 hours (i.e., randomization as well as completion of screening and baseline will all occur the same day). The time window for initiation of study intervention relative to randomization will be 4 (four) weeks.

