6.2.4 Followup Visits

The following study visits must be performed on the weeks indicated above in the Schedule of Evaluations (please see Section 6.1) plus/minus 5 (five) *working* days (i.e., Monday through Friday, not including weekends and holidays):

- Visit 1:
 - Informed Consent Form
 - Medical History Form
 - Inclusion/Exclusion criteria form
 - Enrollment/Randomization form
 - MRI Screening Form & urine pregnancy test
 - MRI brain scan
 - Demographics assessment (electronically in Qualtrics)
 - SDQ assessment (electronically in Qualtrics)
 - Baseline Checklist
- Visit 2 through Visit 13:
 - Child Session Rating Scale (CSRS)
 - Child Outcome Rating Scale (CORS) including the question: "Has there been any significant unfavorable change in your mental or physical health since last class?" (please see Appendix. Not a source document.)
 - Adverse Events (if answered Yes the question above in CORS)
 - Serious Adverse Events (if answered Yes to the SAE question in the Adverse Event form)
 - On Study Visit Checklist Form (modified to include Treatment Administration information)

6.2.5 Completion/Final Evaluation.

The following assessments will be performed at the participant's final visit (Visit 14):

- SDQ assessment (electronically in Qualtrics)
- MRI Screening Form & urine pregnancy test
- MRI brain scan
- Child Outcome Rating Scale (CORS) including the question: "Has there been any significant unfavorable change in your mental or physical health since last class?" (please see Appendix. Not a source document.)
- Adverse Events (if answered Yes the question above in CORS)
- Serious Adverse Events (if answered Yes to the SAE question in the Adverse Event form)
- Study Completion form.

For study participants who discontinue the study intervention early, all of the following assessments will be performed:

- SDQ assessment (electronically in Qualtrics)
- MRI Screening Form & urine pregnancy test
- MRI brain scan
- Child Outcome Rating Scale (CORS) including the following question: "Has there been any significant unfavorable change in your mental or physical health since last class?" (please see Appendix. Not a source document.)
- Adverse Events (if answered Yes the questions above in CORS)
- Serious Adverse Events (if answered Yes to the SAE question in the Adverse Event form)
- Study Completion form.

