Emotional Problems. Our hypothesis is that training will improve emotional problems as assessed by the SDQ T-score compared with controls. We will use an analysis of covariance (ANCOVA) accounting for sex and fit by maximum likelihood. Stata (College Station, TX) will be used to perform data analyses. We will additionally explore age, pubertal status (as determined by the Tanner stage self-report form (Tanner et al., 1962)), and pre-training associations with the changes through an examination of interaction. Potential pre-/post-training differences in movement during MRI will be accounted for by assessing the number of rejected diffusion directions. Sex as a biological variable: In all analyses described, sex will be included as a factor, we will also test for a randomized arm by sex interaction.

In addition, we will examine relationship between changes in node strength of the putamen and changes in emotion by performing a Spearman rank correlation change in node strength through 12 weeks with change in SDQ through 12 weeks.

Other outcomes.

Adherence. We summarize adherence to training including (i) tabulating the number of participants on the training arm who complete at least 75% of sessions, (ii) calculate the minimum, maximum, median and interquartile range of sessions attended by those randomized to the TARA training arm.

Safety and tolerability of the intervention. Adverse events of grade 2 or higher will be tabulated between the arms and compared by the Fisher exact test. Tolerance scores on the CSRS will be summarized (minimum, maximum, median, interquartile range) at each study visiting on the TARA training arm.

We will tabulate the proportion of participants who are retained through 12 weeks and complete the MRI exam and SDQ questionnaire. These will be compared between the arms by the Fisher exact test.

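### The SDQ analysis repeats the MRI-motion adjustment from the imaging analysis, where it corrects no artefact and could bias the treatment comparison

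*Combined protocol and SAP*

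**What the plan says.** Section 9.6, Secondary Outcome, sets the hypothesis for the questionnaire: "Our hypothesis is that training will improve emotional problems as assessed by the SDQ T-score compared with controls". It names the model: "We will use an analysis of covariance (ANCOVA) accounting for sex and fit by maximum likelihood". After a sentence on exploratory interactions with age, pubertal status and pre-training values, the same paragraph adds: "Potential pre-/post-training differences in movement during MRI will be accounted for by assessing the number of rejected diffusion directions". That sentence appears word for word in the Primary Outcome part of Section 9.6, with near-identical text around it.

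Other relevant places:

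- **Collection of the SDQ.** Sections 6.2.4, 6.2.5 and 10.1 describe it as an electronic questionnaire, listed separately from the scan at the final visit.
- **Timing of the scans.** Section 6.2.2 puts the first scan at baseline (Visit 1) and the second at Visit 14. It says that "randomization as well as completion of screening and baseline will all occur the same day".
- **Participants without a second scan.** Section 4.2 lets intervention participants who become pregnant after the first scan finish the training, but the investigators will "not allow participants who become pregnant during the study after the first MRI scan to have the second MRI scan".
- **Population.** Section 9.3 defines intent to treat as everyone randomized.
- **Missing data.** The Primary Outcome text says "The use of maximum likelihood mitigates susceptibility to missing data". The SDQ paragraph repeats the choice of maximum likelihood but not this sentence. Neither part gives a rule for a missing motion value.

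**The concern.** Rejected diffusion directions describe the quality of a diffusion scan. They can distort a node-strength estimate, so the sentence makes sense for the primary outcome. They play no part in how a questionnaire is scored, and the plan gives no reason to carry them into the SDQ analysis.

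Two consequences are possible if an analyst acts on the sentence. First, a pre-to-post difference in movement uses the Visit 14 scan, so part of the adjustment variable is observed after randomization. Conditioning a randomized comparison on such a variable can move the estimated treatment effect, and here there is no measurement error to remove in return. Second, the variable does not exist for someone without a second scan. Depending on how the model is fitted, an SDQ result that the trial holds might go unused.

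The SDQ is the only secondary efficacy outcome, so its analysis set and model terms should not be left to interpretation.

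**Working it through.** **1. The two uses of the sentence compared**

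| | Putamen node strength | SDQ |
|---|---|---|
| Source of the outcome | Diffusion MRI | Electronic questionnaire |
| Can scan motion distort the measurement? | Yes | No |
| Is the Visit 14 scan needed to obtain the outcome? | Yes | No |
| Model terms named | Baseline node strength, arm, sex (Section 9.2) | Sex; arm implied by the comparison (Section 9.6) |
| Is motion listed as a model term? | No | No |

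For node strength, anyone without a second scan already lacks the outcome, so needing a motion value excludes nobody further. For the SDQ it might.

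**2. Effect of adjusting for a post-randomization variable**

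In SD units, let motion be M = a·T + u and the SDQ be Y = d·T + ρ·u + e, where T is the arm. Substituting u = M − a·T gives Y = (d − a·ρ)·T + ρ·M + e. The treatment coefficient therefore shifts by −a·ρ. The documents give neither a nor ρ, so the values below are assumptions:

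- a = 0 or ρ = 0: no shift
- a = 0.2, ρ = 0.1: shift of 0.02 SD in size
- a = 0.2, ρ = 0.3: 0.06 SD
- a = 0.4, ρ = 0.1: 0.04 SD
- a = 0.4, ρ = 0.3: 0.12 SD

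**3. The plan's own sample size**

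The inputs from Section 9.2 are two-sided alpha 0.05, power 80%, d = 0.6 and 10% attrition, all set for putamen node strength.

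- Normal approximation: n = 2·(1.960 + 0.842)² / 0.6² = 43.6, so 44 per arm.
- Two-sample t-test: 44.59, so 45 per arm.
- With attrition: 45 / 0.9 = 50 per arm.

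The plan's 45 and 50 reproduce.

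**4. Illustrative loss if motion were a complete-case covariate**

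The assumptions are that d = 0.6 also holds for the SDQ (the plan gives no SDQ effect size or power) and that 45 per arm have a Visit 14 SDQ (50 less 10%). A share f of them has no second scan. Then n = 45·(1 − f), and power is that of a two-sample t-test with noncentrality 0.6·√(n/2).

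| f | n per arm | Noncentrality | Power |
|---|---|---|---|
| 0% | 45 | 2.85 | 80.4% |
| 10% | 40 (from 40.5) | 2.68 | 75.5% |
| 20% | 36 | 2.55 | 70.9% |

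The normal approximation gives 81.2%, 76.5% and 72.1%.

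**The case against.** A reader might infer that the plan drops everyone without a second scan. The documents do not say so. The SDQ model is described only as accounting for sex, and the motion sentence names no covariate, exclusion or complete-case rule. Even for the imaging outcome, Section 9.2 lists the model terms without motion, and Section 9.3 keeps all randomized participants. Exclusion needs two steps that the plan leaves open: motion entered as a covariate, and missing motion values handled by complete case. A maximum likelihood fit that models missing covariates would keep these participants; an ordinary fit would not. This part of the objection stands, and the loss of data is conditional.

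It is also fair to say that the sentence looks copied over, and that the Secondary Outcome text does contain one analysis where motion could matter: the Spearman correlation of node-strength change with SDQ change. That correlation is in the next paragraph and the sentence is not tied to it, so it does not explain the sentence's place among the ANCOVA instructions. It does bear on the remedy, because motion handling may be wanted there.

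The size is uncertain as well. A 10% to 20% share would match or exceed the 10% attrition that Section 9.2 allows for all causes, and both assessments belong to the same visit. Pregnancy is the only explicitly foreseen route to an SDQ without a second scan, and no number is given. Braces are a listed contraindication and MRI screening is repeated at Visit 14, so other routes are possible but not described.

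Two further inferences go too far. The motion measure is not wholly post-randomization, because its pre-training part comes from the baseline scan. Nor do the documents show that training changes movement in the scanner: restlessness appears only as a possible adverse effect (Sections 5.1 and 7), with no link to rejected directions or to the SDQ.

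**Conclusion.** The concern holds in a limited form. Section 9.6 places an imaging-quality rule inside the SDQ analysis, and no reading gives it a valid role in the arm comparison. If it means adjustment, it corrects no artefact and could shift the treatment effect: by nothing if motion is unrelated to either arm or SDQ, and by 0.02 to 0.12 SD over the non-zero values assumed above. If it does not mean adjustment, it has no function there and leaves analysts an undeclared choice.

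Loss of SDQ records is possible but not prescribed. It is nil if every SDQ completer has a second scan. The fall from about 80% power to about 76% to 71% rests on complete-case handling, a 10% to 20% share, 45 completers per arm and a borrowed d = 0.6, none of which the documents establish for the SDQ.

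The importance is low: it concerns a secondary outcome, probably arises from a carried-over sentence, and changes no figure stated in the plan.

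**What to change.** In Section 9.6:

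1. Remove the motion sentence from the Emotional Problems paragraph, so that it is not part of the SDQ ANCOVA.
2. If motion handling is wanted for the correlation between node-strength change and SDQ change, state it in that paragraph and say how it is done.
3. Add that the SDQ analysis includes every randomized participant with a Visit 14 SDQ, whether or not a second scan was obtained.

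The cost is an edit of two or three sentences, to be made before the database is locked and the analysts are unblinded. Data collection, sample size and the primary analysis are unchanged.
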